11. CRITERIA FOR EVALUATION/REMOVAL FROM STUDY

Definitions Associated with Response Evaluation Criteria in Solid Tumors (RECIST) version 1.

Measurable disease - At baseline, tumor lesions/lymph nodes will be categorized measurable or non-measurable as follows:

11.1 Measurable

Tumor lesions – Must be accurately measured in at least one dimension (longest diameter in the plane of measurement is to be recorded) with a minimum size of:

- 10 mm by CT scan (CT scan slice thickness no greater than 5 mm)
- 10 mm caliper measurement by clinical exam (lesions which cannot be accurately measured with calipers should be recorded as non-measurable)
- 20 mm by chest X-ray

Malignant lymph nodes:

To be considered pathologically enlarged and measurable, a lymph node must be ≥ 15 mm in *short* axis when assessed by CT scan (CT scan slice thickness recommended to be no greater than 5 mm). At baseline and in follow-up, only the *short* axis will be measured and followed.

11.2 New Lesions

There are no specific criteria for the identification of new radiographic lesions; however, the finding of a new lesion should be unequivocal: i.e. not attributable to differences in scanning technique, change in imaging modality or findings thought to represent something other than tumor (for example, some ‘new’ bone lesions may be simply healing or flare of pre-existing lesions). This is particularly important when the patient’s baseline lesions show partial or complete response. For example, necrosis of a liver lesion may be reported on a CT scan report as a ‘new’ cystic lesion, which it is not.

A lesion identified on a follow-up study in an anatomical location that was not scanned at baseline is considered a new lesion and will indicate disease progression. An example of this is the patient who has visceral disease at baseline and while on study has a CT or MRI brain ordered which reveals metastases. The patient’s brain metastases are considered to be evidence of PD even if he/she did not have brain imaging at baseline.

If a new lesion is equivocal, for example because of its small size, continued therapy and follow-up evaluation will clarify if it represents truly new disease. If repeat scans confirm there is definitely a new lesion, then progression should be declared using the date of the initial scan.

11.3 Evaluation of best overall response

The best overall response is the best response recorded from the start of the treatment until disease progression/recurrence (taking as reference for PD the smallest measurements recorded since the treatment started). The patient’s best overall response assignment will depend on the findings of both target and non-target disease and will also take into consideration the appearance of new lesions.

Target Lesions	Non-Target Lesions	New Lesion?	Best Overall Response
-----------------------	---------------------------	--------------------	------------------------------

Protocol Version Date:
October 2, 2019

CR	CR	No	CR
CR	Non CR/ Non PD	No	PR
CR	Not evaluated	No	PR
PR	Non-PD or not all evaluated	No	PR
SD	Non-PD or not all evaluated	No	SD
Not all evaluated	Non-PD	No	NE
PD	Any	Yes or No	PD
Any	PD	Yes or No	PD
Any	Any	Yes	PD

Patients with a global deterioration of health status requiring discontinuation of treatment without objective evidence of disease progression at that time should be classified as having “symptomatic deterioration”. Every effort should be made to document the objective progression even after discontinuation of treatment.

In some circumstances it may be difficult to distinguish residual disease from normal tissue. When the evaluation of complete response depends on this determination, it is recommended that the residual lesion be investigated (fine needle aspirate/biopsy) to confirm the complete response status.

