2.2 Secondary Objectives

1. To describe the adverse events associated with FOLFIRINOX when administered preoperatively in patients with resectable pancreatic cancer.
2. To estimate the fraction of patients who can successfully undergo surgery after neoadjuvant chemotherapy.
3. To estimate the overall resectability rate, rate of R0 resection, disease free survival (DFS), overall survival (OS), overall response rate (ORR; complete response (CR) + partial response (PR)), and disease control rate (DCR; CR + PR + stable disease (SD)) after administration of FOLFIRINOX in patients with resectable pancreatic cancer.

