7. TREATMENT PLAN

7.1 Treatment Dosage and Administration

Patients on this trial will be treated with neoadjuvant FOLFIRINOX for 2 cycles (1 cycle = 28 days). Patients will receive FOLFIRINOX on an outpatient basis on days 1 and 15 of each cycle. Following neoadjuvant treatment, patients will undergo repeat imaging (CT or MRI) to be reassessed for resectability of the tumor. Further adjuvant treatment will be determined at the treating physician's discretion (i.e. chemoradiotherapy or adjuvant chemotherapy). It is important to note that post-neoadjuvant therapy is determined by the treating physician per their institutional guidelines and standard of care. While this study will collect data regarding disease progression and survival from the post-neoadjuvant period, this protocol does not dictate post-neoadjuvant treatment which may be done at other institutions.

For patients with an R1 resection, any chemoradiotherapy will be included in the 24 weeks of perioperative therapy. Chemoradiotherapy and the timing in which it will be given will be determined at the treating physician's discretion based on margin status and the patient's recovery. Furthermore, patients who receive chemoradiotherapy may also receive adjuvant chemotherapy; however, this will be based on the treating physician's discretion. Recommended radiosensitization will be through 5FU 200 mg/m²/Day continuous infusions M-F of each week or capecitabine 825 mg/m² PO BID M-F for the duration of radiation therapy. Patients who

receive adjuvant therapy will receive treatment based upon treating physician's discretion with a recommended duration of therapy lasting 6 months accounting for preoperative therapy.

The neoadjuvant FOLFIRINOX regimen starting doses are: oxaliplatin 85 mg/m², followed by leucovorin 400 mg/m² given simultaneously with irinotecan 180 mg/m², followed by 5FU 400 mg/m² bolus and then 2400 mg/m² (Table 1). Patients require a PORT, PICC or other IV access to allow administration of 5FU via a continuous infusion pump. All agents should be administered within SOC drug administration guidelines. Appropriate dose modifications for each agent are described in Section 9.0. See drug monographs/package inserts for full details on each agent.

Agent	Dose*	Route	Schedule
Oxaliplatin	85 mg/m ² in 250 cc D5W	IV before irinotecan	Day 1,15 of each 28 day cycle

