9.2 Surgical Resection

Approximately 4 weeks (+/- 2 weeks) after the completion of the neoadjuvant treatment, patients will undergo standard of care operative exploration and complete extirpative surgery. Operative planning will be based on the original review of the patients' initial (i.e. pre-treatment) staging CT or MRI scan and the scan obtained after completion of the neoadjuvant protocol. All patients will undergo two modalities of operative exploration for occult metastatic disease undetectable with conventional cross-sectional imaging. Prior to laparotomy, patients will undergo a formal two-port staging laparoscopy to exclude the presence of occult metastatic disease involving the liver or peritoneal surfaces. Suspicious nodules possibly representing metastatic disease will be biopsied to confirm a pathologic diagnosis of metastatic pancreatic adenocarcinoma. Proof of metastatic cancer (i.e. stage IV cancer) will exclude patients from operative resection of the primary pancreatic cancer. In the absence of metastatic disease detectable with staging laparoscopy, patients will undergo a formal laparotomy with abdominal exploration to exclude occult metastatic disease involving the peritoneal surfaces or liver.

In the absence of occult metastatic disease, patients will undergo the planned operative procedure to resect the primary pancreatic adenocarcinoma completely. Based on preoperative imaging,

patients will undergo either a pancreatoduodenectomy (PD) or distal pancreatectomy and splenectomy (DPS). PD will be performed for patients with head and/or neck of pancreas cancers. DPS will be performed for patients with body and/or tail of pancreas cancers. PD and DPS will be performed according to standardized techniques which are employed routinely at Indiana University Hospital.

All margins of resection will be sampled intraoperatively to ensure complete clearance. For PD, the neck of pancreas and bile margins will be reviewed with frozen section histopathologic analysis. For DPS, the proximal pancreatic margin (i.e. body or neck of pancreas) will be reviewed intraoperatively. Final margin status (R0 versus R1) of the resected specimens will be recorded in addition to the intraoperative margin status assessments.

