10. STUDY CALENDAR

1 cycle = 2 treatments over 28 days (treatments are given every 2 weeks) D1=Day 1 D15=Day 15	Baseline ¹	Cycles 1-2		Surgical Evaluation/EOT ²	Long-term Follow-up ⁹ Post-neoadjuvant tx
	-28 days	Day of Cycle (± 7 days)		4 (+/- 2) weeks post neoadjuvant tx	
		D1	D15		
REQUIRED ASSESSMENTS					
Medical history	X				
Height	X				
Physical examination	X	X	X		
BP, weight	X	X	X		
ECOG performance status	X	X	X		
Complete metabolic panel	X	X	X		
Calculated creatinine clearance	X	X	X		
Platelets, ANC & Hgb	X	X	X		
CA 19-9	X				
Urine pregnancy ³	X				
AE and concomitant medication assessment	X	X	X	X ¹⁰	
Overall survival					X
Disease progression					X
DISEASE ASSESSMENT					
MRI or CT chest, abdomen, pelvis	X			X ⁵	X ⁴
Surgical resection (if applicable)				X	
TREATMENT					
Neoadjuvant FOLFIRINOX		X	X		
CORRELATIVE STUDIES					
Tissue collection	X ⁶			X	
Blood collection	X ⁶			X	
ASSESSMENTS					
PG-SGA questionnaire	X ⁷			X ⁸	
FAACT questionnaire	X ⁷			X ⁸	

Calendar Footnotes:

¹ Baseline assessments performed within 7 days of Cycle 1 Day 1 do not need to be repeated.

² All patients will have a surgical evaluation visit 4 (+/-2) weeks of completing or discontinuing neoadjuvant chemotherapy as part of their routine care. Information collected during this visit will be used for the EOT visit for this study.

³ Required only for women of child-bearing potential.

⁴ Disease progression will be assessed via radiology report from any MRI or CT scans done during the follow-up period per standard of care.

⁵ Repeat imaging may be performed prior to surgical resection at the treating physician's discretion.

⁶ Whenever possible

⁷ PG-SGA and FAACT assessments not completed at baseline can be completed on C1D1 as long as they are done before treatment begins.

⁸ PG-SGA and FAACT assessments should be completed within 4 (+/-2) weeks of completing or discontinuing neoadjuvant chemotherapy.

⁹ Follow-up for survival and disease progression will be done every 3-6 months years 1-3, every 6 months years 4-5, and every 12 months thereafter.

¹⁰ May be done by telephone in lieu of an in-person visit.

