14.3 Statistical analysis plan

Primary Outcome:

- Pathologic complete response: the proportion of the 48 patients having a pathologic complete response with a 95% confidence interval (using normal approximation) will be calculated.

Secondary Outcomes:

- *Safety:* Adverse events of grades 3, 4, 5 by the CTCAE v4.3 criteria for each category listed in section 2.1.6 will be summarized. The proportion of patients with each category of AE will be calculated with a 95% confidence interval. After the enrollment of the first 20 patients, we will evaluate the rate of surgical resection. If >6 patients are not able to proceed with surgery due to excessive toxicity or progression (not including occult metastatic peritoneal disease that was found during surgery and not on imaging) the study will discontinue due to unacceptable toxicity.

- *Ability of patients to undergo surgical resection after receiving neoadjuvant FOLFIRINOX*: the proportion of patients who are able to go through surgery among those who have resectable tumor will be calculated accompanied with a 95% confidence interval.
- *Rate of resectability* will be evaluated by determining the proportion of patients who are able to undergo surgery with resection of their primary tumor (R0 vs R1) resection. A 95% confidence interval will be constructed for the rate.
- *Disease free survival (DFS)*: DFS is defined as time from registration to evidence of tumor recurrence (including clinical deterioration related to the underlying pancreatic cancer, as assessed by the investigator) or death from any cause. Kaplan-Meier curve for DFS will be plotted. Median DFS time will be calculated accompanied with a 95% confidence interval.
- *Overall survival*: time from registration to death for 48 patients with right censoring will be analyzed using Kaplan-Meier estimate. Median survival time will be obtained accompanied with a 95% confidence interval.
- *Objective response rate*: proportion of patients with complete responses (CR) or partial responses (PR) after 4 cycles of FOLFIRINOX treatment will be constructed with a 95% confidence interval.
- *Disease control rate*: Proportion of patients with complete responses (CR), partial responses (PR), or stable disease (SD) after 4 cycles of FOLFIRINOX treatment will be obtained with a 95% confidence interval.

Tertiary Outcomes:

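### The scan that feeds ORR is not fixed: the response window stays open past resection, and the four-cycle time point does not match the two-cycle course

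*Combined protocol and SAP*

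**What the plan says.** Section 11.3 holds the protocol's rule for combining lesion findings into CR, partial response (PR), stable disease (SD) or progression: "The best overall response is the best response recorded from the start of the treatment until disease progression/recurrence". Nothing in section 11 ends that window at surgery or at later treatment, or says how to code a target lesion that has been removed.

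Section 9.2 plans surgery about 4 (±2) weeks after neoadjuvant treatment, when "patients will undergo standard of care operative exploration and complete extirpative surgery". Section 7.1 leaves later chemotherapy or chemoradiotherapy to the treating physician.

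The response endpoints are described in two places:
- Section 2.2 asks for ORR and DCR "after administration of FOLFIRINOX in patients with resectable pancreatic cancer".
- Section 14.3 defines ORR as the "proportion of patients with complete responses (CR) or partial responses (PR) after 4 cycles of FOLFIRINOX treatment" and DCR as the "Proportion of patients with complete responses (CR), partial responses (PR), or stable disease (SD) after 4 cycles of FOLFIRINOX treatment".

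The treatment plan in section 7.1 reads "Patients on this trial will be treated with neoadjuvant FOLFIRINOX for 2 cycles (1 cycle = 28 days", with dosing on days 1 and 15.

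On imaging, section 7.1 says "Following neoadjuvant treatment, patients will undergo repeat imaging (CT or MRI) to be reassessed for resectability of the tumor", while footnote 5 of the study calendar (section 10) leaves repeat pre-operative imaging to the physician's discretion. Footnote 4 says of later scans: "Disease progression will be assessed via radiology report from any MRI or CT scans done during the follow-up period per standard of care".

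**The concern.** A best-response window that runs to progression suits a trial in which the tumour stays in place. Here surgery removes the target lesion. Consider a patient with SD at restaging who is resected and then has a clean scan. That patient fits the row of the section 11.3 table with target CR, non-target CR and no new lesion, which gives CR. If non-target disease was not evaluated, the table gives PR, which also counts towards ORR. Responses to post-operative therapy fall in the same window.

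ORR and DCR are named secondary objectives with planned 95% confidence intervals, and section 14.3 also relates biomarkers to other response outcomes. A response created by the operation would carry into those analyses. Two analysts following the text could report quite different ORRs.

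**Working it through.** **1. The plan's own figure.** No design figure is given for ORR, DCR or the resection rate. The only one is 82% power for pCR (43 evaluable, 1% versus 10%, two-sided 5%). An exact binomial test rejecting at 3 or more pCRs of 43 has power 81.8% and type I error 0.9%; rejecting at 2 or more would give 6.9%. The stated power is reproduced, and it does not depend on radiologic response.

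**2. Where the section 14.3 time point falls.**
- Planned course: 2 × 28 = 56 days, so cycle 2 ends at week 8.
- Surgery 4 (±2) weeks later: weeks 10 to 14.
- Four cycles read literally: 4 × 28 = 112 days, or week 16, which is after surgery.
- Four cycles read as four treatments: days 1, 15, 29 and 43, so the assessment is pre-operative.

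The two readings put the scan on opposite sides of the operation. Section 8 and the Table 4 footnotes refer to six cycles, so the meaning of the word cannot be settled from the text.

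**3. Whether a pre-operative scan must exist.** Section 7.1 has it as planned; calendar footnote 5 makes it discretionary. Section 14.2 asks for at least one post-baseline assessment without saying when. A patient whose first post-baseline scan is post-operative could therefore be counted as evaluable.

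**4. Illustration for ORR.** Let rr be the pre-operative response rate, s the fraction resected, and f the share of resected patients coded CR from a later scan. Assume response is independent of resection. Then

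ORR = rr + (1 − rr) × s × f

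Inputs: rr = 31% (the FOLFIRINOX rate in section 1.1); s = 9/16 = 56% and 20/25 = 80% (the resected fractions in the nab-paclitaxel/gemcitabine studies in section 1.3). All are assumptions for this trial.

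| f | s = 56% | s = 80% |
|---|---|---|
| 0.25 | 0.31 + 0.69 × 0.5625 × 0.25 = 41% | 0.31 + 0.69 × 0.80 × 0.25 = 45% |
| 0.50 | 50% | 59% |
| 1.00 | 0.31 + 0.69 × 0.5625 = 70% | 0.31 + 0.69 × 0.80 = 86% |

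Read before surgery only, ORR stays at 31%. With rr = 10% and s = 80%, the range is 28% (f = 0.25) to 82% (f = 1).

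**5. Illustration for DCR.** A resected patient with SD or better before surgery is already counted, so recoding SD as CR changes nothing. Let g be the share of resected patients not evaluable (NE) before surgery, and assume 30% disease control in unresected patients. With s = 80%:
- Pre-operative reading: 0.80 × (1 − g) + 0.20 × 0.30, which is 86% at g = 0, 78% at g = 0.10 and 66% at g = 0.25.
- Open-window reading: 0.80 + 0.06 = 86% throughout.

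The change is zero when every resected patient has an evaluable pre-operative scan without progression.

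**The case against.** The strongest reply is that section 14.3 never calls ORR or DCR best response. It ties both to a FOLFIRINOX time point, section 2.2 points the same way, and two 28-day cycles do contain four treatments. Footnote 4 names follow-up scans as the source for progression, and section 7.1 describes post-neoadjuvant data collection as progression and survival. Section 11.4.3 adds that raised markers must normalise before CR, while the calendar schedules CA 19-9 at baseline only. ORR and DCR are also absent from the outcome measures in section 3.2 and drive no decision.

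Much of this stands. It rules out a reading that a reader might infer: that ORR and DCR will be driven up to the resection rate, with ORR at least 56% to 80%. That floor needs every resected patient to be coded CR; at f = 0.25 and 56% resected, the figure is 41%. The resection fractions come from a different regimen. DCR mostly does not move. Nor do the documents plan a comparison with the 31% rate, or label it as RECIST where they cite it.

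The reply does not close the gap. The time point is pre-operative only if cycles is read as treatments. Footnote 4 gives follow-up scans a use without excluding another. The marker condition covers only markers raised at baseline. Section 2.2 sets a start for the assessment but no end.

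**Conclusion.** The point holds as an unresolved definition that can bias ORR. Sections 7.1, 10, 11.3 and 14.3 together do not determine which scan is used, and one permitted reading counts surgical removal as response. Under the stated assumptions the excess over 31% runs from about 10 points (41%) to about 55 points (86%). This is an illustration, since the documents assume neither rate, and the excess is nil if only the pre-operative scan is read. DCR is affected only through resected patients without an evaluable pre-operative scan. The pCR endpoint and its 82% power are untouched. The change should be made because it protects a named secondary objective at almost no cost.

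**What to change.** Add to section 11.3 and to the ORR and DCR entries in section 14.3, in words such as: *Response is read only from imaging between the start of FOLFIRINOX and the last scan before resection, and before any anticancer therapy outside the protocol. Later scans inform recurrence and progression only. Patients without an evaluable scan in this window are NE under section 11.3.1 and remain in the denominator.*

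Two conflicts must also be reconciled: four cycles in section 14.3 against two in section 7.1, and repeat imaging as planned in section 7.1 against discretionary in calendar footnote 5. The new sentence alone would leave both in place.

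The cost is a few lines of text. The downside is a lower, less favourable ORR, because patients with no pre-operative scan count as non-responders. How many there are depends on how the imaging passages are reconciled.

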11.3.1 Missing assessments and in-evaluable designation

When no imaging/measurement is done at all at a particular time point, the patient is not evaluable (NE) at that time point. If only a subset of lesion measurements are made at an assessment, usually the case is also considered NE at that time point, unless a convincing argument can be made that the contribution of the individual missing lesion(s) would not change the assigned time point response. This would be most likely to happen in the case of PD.

11.3.2 Definitions of Pathological Response

Histopathologic response after neoadjuvant therapy will be evaluated according to the Evan’s criteria as detailed below. The evaluation includes assessment of the amount of variable carcinoma remaining in conjunction with cytologic changes.

Evans’ criteria for pathologic response following neoadjuvant therapy (22)	
Grade	Tumor regression
I	<10% to no tumor cells destroyed
II	IIa: 10-50% of tumor cells destroyed
	IIb: 50-90% of tumor cells destroyed
III	>90% of tumor cells destroyed
	IIIM: sizable pools of cellular mucin
IV	No viable tumor cells
	IVM: Acellular pools of mucin

11.4 Methods of Measurement

Imaging based evaluation is preferred to evaluation by clinical examination. The same imaging modality must be used throughout the study to measure disease. All measurements should be
Protocol Version Date:

October 2, 2019

recorded in metric notation, using calipers if clinically assessed. All baseline evaluations should be performed as close as possible to the treatment start and never more than 4 weeks before the beginning of the treatment.

11.4.1 CT and MRI

CT is the best currently available and reproducible method to measure lesions selected for response assessment. Measurability of lesions on CT scan based on the assumption that CT slice thickness is 5mm or less. When CT scans have slice thickness greater than 5 mm, the minimum size for a measurable lesion should be twice the slice thickness. MRI is also acceptable in certain situations (e.g. for body scans).

